## **2.11. Primary Patency**

A Kaplan-Meier (KM) survival curve for primary patency will be estimated for enrolled patients who received PhotoFix for any non-CEA procedure. Additional KM plots for primary patency may be estimated by surgical indication but will be determined by the sample size of each subgroup; sample sizes of 20 patients or more will be considered to estimate meaningful plots.

## **2.12. Overall Survival**

Frequency counts and percentages will be presented in a table for enrolled patients. A KM survival curve for overall survival will be estimated for all enrolled patients. Additional KM plots for survival may be estimated by mortality category (all-cause mortality, vascular-related mortality, and device-related mortality) but will be determined by the sample size of each subgroup; however, it is unlikely that the sample size will be large enough for subgroup analysis.

## **2.13. All-Cause Reoperation Rate**

Frequency counts and percentages will be presented in a table for enrolled patients. A KM survival curve for freedom from reoperation will be estimated for all enrolled patients. Additional KM plots for freedom from reoperation may be estimated by surgical indication but will be determined by the sample size of each subgroup; however, it is unlikely that the sample size will be large enough for subgroup analysis.

## **2.14. Device-Related Reoperation Rate**

Frequency counts and percentages will be presented in a table for enrolled patients. A KM survival curve for freedom from device-related reoperation will be estimated for all enrolled patients. Additional KM plots for freedom from device-related reoperation may be estimated by surgical indication but will be determined by the sample size of each subgroup; however, it is unlikely that the sample size will be large enough for subgroup analysis.

## **2.15. Explant Rate**

Frequency counts and percentages will be presented in a table for enrolled patients. A KM survival curve for freedom from explant will be estimated for all enrolled patients. Additional KM plots for freedom from explant may be estimated by surgical indication but will be determined by the sample size of each subgroup; however, it is unlikely that the sample size will be large enough for subgroup analysis.

## **2.16. Restenosis Rate**

Frequency counts and percentages will be presented in a table for enrolled patients. A KM survival curve for freedom from restenosis ( $\geq 50\%$ ) will be estimated for all enrolled patients. Additional KM plots for freedom from restenosis ( $\geq 50\%$ ) may be estimated by surgical indication but will be determined by the sample size of each subgroup; however, it is unlikely that the sample size will be large enough for subgroup analysis.

## **2.17. Adverse Events**

Adverse events will not be coded. The incidence of adverse events will be summarized for the aggregate sample. Adverse events will be considered as any event happening during or after PhotoFix implant. Any adverse event that occurs prior to surgery will not be included in the summary or analysis.

Adverse events will be summarized based on timing, in relation to surgery. Events will be categorized as early if the event occurs  $< 30$  days after surgery, while late post-operative events will be considered as events occurring  $\geq 30$  days after surgery.

Adverse events will be summarized by pre-specified category; events classified as other will be manually classified, as deemed appropriate. The following will be included in the summary of adverse events: consequence of event, required drug treatment or intervention, severity, relation to surgery, relation to PhotoFix, and status of event at end of study. Events deemed to be related to PhotoFix, with any definitive assessment, will be summarized in a frequency table; additional information discovered during event investigation will be described, as deemed necessary.

Adverse event rate will be presented as frequency counts and percentages in a table for enrolled patients. Adverse events will be presented in aggregate and by surgical indication.

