Patient demographics and medical history, including medications, comorbidities, pertinent surgical history, and fundamental vascular diagnosis, will be collected at time of consent. Medications will only include drugs of interest and will not require a complete listing. Adverse events will be collected after surgery on all patients consented and enrolled into the study. The investigation will be conducted for a period necessary to collect all follow-up, as needed on each patient, but will not exceed 7 months after surgery. The total time a patient will be followed will be determined by their date of surgery; dates of surgery should occur within 60 days of consent. If the patient's surgery is scheduled after 60 days, a re-screen request must be submitted to the Sponsor. The anticipated final follow-up will be conducted in November 2019, but will ultimately be determined by IRB approvals, site activation, and by rate of patient enrollment.

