6.1 Study Endpoints & Variables

In the case of CEAs, the primary endpoint of the study will be rate of ipsilateral central neurologic events.

- Ipsilateral central neurologic events: Transient ischemic attack, amaurosis fugax, stroke, and symptomatic carotid occlusion.

In the case of all other (non-CEA) vascular procedures, the primary endpoint of the study will be primary patency in the target artery or vein.

- Primary patency (of target vessel): Loss of patency will be determined by the loss of previously palpable pulses, patients presenting with recurrent symptoms, a drop in ABI >0.15 in the case of lower limb artery repair, Doppler ultrasound findings of occlusion, angiography of the affected vessel or a combination of these.

The secondary endpoints of the study will include: overall survival rate, all-cause reoperation rate, device-related reoperation rate, explant rate, restenosis rate, adverse event rate, and secondary patency (HAR only).

- Overall Survival:
 - Early mortality: Death < 30 days following PhotoFix implantation.
 - Late mortality: Death ≥ 30 days following PhotoFix implantation, until last day of follow-up.
- All-Cause Reoperation Rate: The total number of reoperations required in patients over the follow-up period, which include the repair or alteration of the surgical area around the patch.

- **Device-Related Reoperation Rate:** The total number of unplanned reoperations required in patients over the follow-up period, which are determined by the surgeon to be device-related.
- **Explant Rate:** The total number of device explants over the course of follow-up. Explants will include the removal of PhotoFix for any reason after implantation.
- **Restenosis Rate:** The total number of documented cases of stenosis documented as the recurrence of abnormal narrowing of a vessel after corrective surgery.
- **Adverse Event Rate:** The total number of any unfavorable and unintended sign (including an abnormal laboratory finding), symptom, or disease temporarily associated with the use of a device, whether or not related to the device.
- **Secondary Patency (HAR only):** The time from implantation to the point where the access is abandoned.

Statistical analysis will be used to assess all study endpoints as applicable.

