6.7 Statistical Analysis Plan

Enrolled patients will be described in aggregate and by indication (as deemed appropriate); baseline characteristics will include, but not limited to, age, sex, race, ethnicity, body mass index (BMI), comorbidities, fundamental diagnosis/etiology, and pertinent surgical history. Operative details will be described in aggregate and include a summary of the types of procedures performed, by relevant category. Parameters with continuous data types will be summarized using descriptive statistics, i.e., mean, standard deviation, and range. Categorical clinical parameters will be summarized based on percentages.

Ipsilateral central neurologic event rate, overall survival, re-operation rate, explant rate, and restenosis rate ($\geq 50\%$ stenosis) will be summarized based on percentages of affected patients and included in a table, which will summarize the endpoints in aggregate and by surgical indication (ex. CAS, ESRD, PAD, AAA, etc.). The summary of ipsilateral central neurologic event rates will include all events (transient ischemic attack, amaurosis fugax, stroke, and symptomatic carotid occlusion), as well as the incidence of each event individually.

Additional analysis of follow-up data will also be performed with the Kaplan-Meier method, as deemed appropriate by the incidence of events. Kaplan-Meier plots may be generated for endpoints including overall survival, primary patency, secondary patency, as well as freedom from ipsilateral central neurologic event rate, re-operation, explant, and restenosis ($\geq 50\%$ stenosis). Kaplan-Meier plots for survival will include the following mortality classifications: all causes of mortality, vascular-related mortality and device-related mortality (as applicable). The remaining plots will be specific to indication, if the sample sizes allow for the creation of meaningful plots.

The incidence of adverse events will be categorized and summarized with percentages for the aggregate sample. Adverse events will be divided into early and late post-operative events to represent the distribution of occurrences. Events will be considered as early events if the event occurs <30 days after the operation, while late post-operative events will be considered to be all events happening after this time period. Early and late events will be presented by indication for surgery, seriousness of event, and relation to PhotoFix. Adverse events occurring secondary to

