### 2.9.2 Secondary Analysis

- **Overall Survival:**

- Percent of patients surviving
  - *Early mortality:* Death  $< 30$  days following PhotoFix implantation
  - *Late mortality:* Death  $\geq 30$  days following PhotoFix implantation

- **All-Cause Reoperation Rate:**

- Percent of patients requiring reoperations
  - Reoperation includes the repair or alteration of the surgical area around the patch.

- **Device-Related Reoperation Rate:**
  - Percent of patients requiring unplanned reoperations that are documented as possibly, probably or definitely, device-related
- **Explant Rate:**
  - Percent of patients requiring device explants
    - Explants will include the removal of PhotoFix for any reason after implantation.
- **Adverse Event Rate:**
  - Percent of patients who experienced at least one adverse event
  - Percent of patients who experienced at least one device-related adverse event
- **Restenosis Rate:**
  - Percent of patients who develop stenosis
    - Stenosis is considered as the recurrence of abnormal narrowing of an artery or vein after corrective surgery.
    - Categorization of stenosis  $\geq 50\%$  will occur if data is available.
- (Hemodialysis Access Repair only)  

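### Adverse events are split at day 30 and summarised only as counts and percentages, but the late window holds about five times the patient-time, so the early and late figures are not comparable rates

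*SAP*

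**What the plan says.** Protocol 6.7 gives the purpose of the split: "Adverse events will be divided into early and late post-operative events to represent the distribution of occurrences". It then presents early and late events by surgical indication, seriousness and relation to the device. SAP 2.17 repeats the cut. "Events will be categorized as early if the event occurs" fewer than 30 days after surgery, and "late post-operative events will be considered as events occurring" at 30 days or later.

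The planned summary is "Adverse event rate will be presented as frequency counts and percentages in a table for enrolled patients". SAP 2.9.2 defines the endpoint as "Percent of patients who experienced at least one adverse event", with a second line for device-related events, and neither line is divided by time. SAP 2.2 puts every patient who received the patch into all summaries other than basic demographics. No separate denominator for the early or the late part is stated anywhere.

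Follow-up is about 6 months (Protocol 1.2), with visit windows of 14 days either side (Protocol 3.2) and a ceiling: it "will not exceed 7 months after surgery".

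For every other secondary endpoint the SAP commits to a Kaplan-Meier curve: survival (2.12), all-cause and device-related reoperation (2.13, 2.14), explant (2.15), restenosis (2.16) and secondary patency (2.18). The list of possible Kaplan-Meier plots in Protocol 6.7 does not include adverse events either.

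**The concern.** The split is meant to show when adverse events occur, but the two windows differ greatly in length. The early one is 30 days and the late one about 5 months. A raw late percentage several times the early one could come from a steady hazard, and equal percentages could hide a marked perioperative peak.

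There is a second, smaller issue. If late events are divided by all enrolled patients, the denominator includes patients who had already died or left before the late window opened.

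What is at stake is the reading of the safety table in the final report. Protocol 1.5 says the study is to support surveillance for residual risk, and whether events cluster around surgery or continue afterwards is part of that. The interim report is not affected, because SAP 2.19 plans no breakdown by timing there.

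**Working it through.** **Inputs**
- Early window: 30 days (SAP 2.17).
- End of follow-up, D: 6 months = 182.6 days; 168.6 and 196.6 days at the edges of the visit window (Protocol 3.2); 7-month ceiling, about 213 days.
- Early termination: 10% (Protocol 3.2). Its timing is not given, so it is varied below.

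**The plan's own figure.** The documents give no exposure ratio or adverse event rate to reproduce. The one derived figure that uses the 10% is the number to consent: 100 / [(1 − 0.33)(1 − 0.10)] = 165.8, or 166, as stated. This confirms that the 10% applies to patients who remain after screening.

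**Patient-time ratio, no losses:** (D − 30)/30.

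| D (days) | Late/early |
|---|---|
| 168.6 | 4.6 |
| 182.6 | 5.1 |
| 196.6 | 5.6 |
| 213 | 6.1 |

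**With 10% early termination, D = 182.6**
- Loss at a constant rate: 29.74 early and 143.57 late days per enrolled patient, ratio 4.8. Uniform loss also gives 4.8.
- All losses at day 30: 30 early and 0.90 × 152.6 = 137.34 late days, ratio 4.6.
- Lowest case, D = 168.6 with all losses at day 30: 0.90 × 138.6 / 30 = 4.2. The full range is therefore 4.2 to 6.1.

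**What the percentages would show (assumed hazards)**
- Constant hazard, no losses: 30/182.6 = 16.4% of events fall early and 83.6% late. If the 6-month risk is 20%, λ = −ln(0.80)/182.6 per day. Then 1 − exp(−30λ) = 3.6% of patients have an early event and 1 − exp(−152.6λ) = 17.0% a late one, although the risk never changes.
- Early hazard 5.09 times the late hazard, with 10 late events per 100 patients: 10.0 early and 10.0 late, so the peak does not show.
- Early hazard 10 times the late hazard: 19.7 early and 10.0 late, so 66% of events are early.

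**The same counts as rates** (100 enrolled, 10% loss at a constant rate, 30.44 days per month)
- Early patient-months: 100 × 29.74/30.44 = 97.7. Late: 100 × 143.57/30.44 = 471.6.
- 10 early and 10 late events: 10.2 versus 2.1 per 100 patient-months, a 4.8-fold early excess behind identical percentages.
- 10 early and 50 late events: 10.2 versus 10.6, practically equal rates behind a five-fold difference in counts.

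**Denominator.** With the 10% loss spread over follow-up, about 98% of patients are still followed at day 30, so a late percentage over all enrolled is about 2% too low in relative terms. If every loss came by day 30, 90% would remain and it would be 10% too low.

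**The case against.** The strongest reply is that the study is single-arm and descriptive. No early-versus-late test or hazard statement is planned, the window definitions are stated, and the split simply shows where events fell. That stands. The harm is limited to readers who take the percentages as rates. However, the table's declared purpose is to show the distribution over time, and without exposure it does that poorly.

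Four stronger readings are tempting, and the documents do not support them.
- **A reader might infer that deaths have the same problem**, since they are cut at the same point ("Early mortality: Death < 30 days following PhotoFix implantation") and tabulated as "Percent of patients surviving". SAP 2.12 commits to a Kaplan-Meier survival curve for all enrolled patients, which handles time at risk and censoring.
- **A reader might infer that this table is the only planned account of when complications occur.** Reoperation, explant, restenosis and patency all have Kaplan-Meier curves in the SAP. The gap is in adverse events as a class.
- **A reader might infer that the pattern merely follows window length.** That is so only under a constant hazard. No event rates are given, so the direction and size of any distortion are unknown.
- **A reader might take the enrolled-patient denominator of the early and late parts as stated.** The sentence in SAP 2.17 concerns the overall rate. The shared denominator is a reasonable inference from SAP 2.2 and 2.17, and the bias it adds is small.

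It is also fair to object that simple Poisson intervals on all events would be too narrow, because one patient can have several events, and that many subgroup cells would be sparse. The fix allows for both.

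**Conclusion.** The point holds for adverse events only. The day-30 split is reported without patient-time, number at risk or a time-to-event summary, over windows whose patient-time differs by a factor of about 4.8 to 5.1 (4.2 to 6.1 across the visit window, the 7-month ceiling and the assumed timing of losses). The planned table therefore cannot separate a perioperative peak from a steady hazard. The ratio rests on the stated follow-up and the 10% early termination; the event counts and hazards above are illustrations. This is a minor improvement to the reporting. It changes no primary endpoint, Kaplan-Meier estimate, error rate or decision rule.

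**What to change.** In SAP 2.17, with matching wording in Protocol 6.7, keep the day-30 split and amend the aggregate early/late table as follows:

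- Give early percentages over implanted patients, and late percentages over patients alive and in follow-up at day 30. State both denominators.
- For each window, add patient-months and events per 100 patient-months, counting late time from day 30 to last contact.
- Use intervals that allow for repeat events within a patient, such as a patient-clustered variance or a patient-level bootstrap. Alternatively, report first-event rates per window, with patient-time ending at that event, and exact Poisson intervals.
- Add a Kaplan-Meier or cumulative incidence curve for time to first adverse event.
- Base any statement comparing early with late on the rates.

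The breakdowns by indication, seriousness and device relation can stay as counts and percentages, given sparse cells. No change is needed for deaths.

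The cost is a few lines of SAP text, a slightly busier table, one more curve, and late percentages that rise slightly. No new data are needed: the surgery date, event start date and study exit date are already on the Operative Assessment, Adverse Event and End of Study forms (Protocol Appendix D).

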## **2.18. Secondary Patency**

A Kaplan-Meier (KM) survival curve for secondary patency will be estimated for enrolled patients who received PhotoFix for hemodialysis access repair (HAR).

## **2.19. Interim Analysis**

There is an interim analysis planned for January of 2019. This analysis will be used to assess the interim performance and safety of PhotoFix. The interim analysis report will focus on the summary statistics of all primary and secondary endpoints. Sample size, frequency, and percentages will be presented for categorical variables. Sample size, arithmetic mean, standard deviation, median, minimum and maximum will be presented for continuous variables. Summaries will be presented in tables. The creation of KM plots and sub-analyses by surgical indication, device relation or timing of event are not planned.

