another complication will be collected, but not included in the calculation of adverse event rates. Adverse events occurring prior to PhotoFix implant will not be reported.

An interim analysis of the data will be performed approximately 6 months after the initiation of enrollment. The sample size will be dependent on enrollment rate; follow-up could range from 0 days to 5 months. This analysis will be used to assess the interim performance and safety of PhotoFix. The analysis of this data will also be used to address the planned enrollment of the study and to determine if any modifications to the study are necessary.

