## **2.2. Study Population**

All consented patients will be included in the basic patient demographics summary; this section will include data collected on the Demographics Electronic Case Report Form (eCRF). All patients who receive PhotoFix as part of their vascular repair or reconstruction surgery will be considered enrolled and included in all additional summaries and analyses.

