## 2.9. Definition of Analyses

All analyses will focus on outcomes reported during the follow-up period, after PhotoFix implant. Analyses will summarize data collected through the end of follow-up; analyses at each time point are not planned, unless otherwise indicated.

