## **2.10. Incidence of Central Neurologic Events**

Frequency counts and percentages will be presented in a table for enrolled patients who received PhotoFix during carotid endarterectomy (CEA).

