## **2.21. Handling Missing Data**

Listings will be provided for all data. Descriptive statistics will be provided for all planned visits as provided on the eCRFs.

Data may be entered as unknown and therefore will appear in the data listings as such.

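### SAP 2.19 reports interim endpoints as crude percentages over unequal follow-up, with no fixed-time risk or number at risk, and neither document plans a confidence interval for any rate

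*SAP*

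**What the plan says.** **Interim**
- Protocol 6.7 places the interim about 6 months after enrollment starts. It leaves the number of patients open and says "follow-up could range from 0 days to 5 months". Besides assessing performance and safety, the results are to be "used to address the planned enrollment of the study and to determine if any modifications to the study are necessary".
- SAP 2.19 gives n, counts and percentages for categorical variables, and n, mean, SD, median and range for continuous ones. It then states: "The creation of KM plots and sub-analyses by surgical indication, device relation or timing of event are not planned".
- SAP 2.2 sets the denominator: patients who receive the patch "will be considered enrolled and included in all additional summaries and analyses".
- SAP 2.9 says "analyses at each time point are not planned, unless otherwise indicated", and 2.19 indicates none.
- SAP 2.21 says "Descriptive statistics will be provided for all planned visits as provided on the eCRFs" and promises listings of all data. SAP 1.1 says the document serves both the interim and the final report, so 2.21 can be read as covering the interim.
- SAP 2.9.1 defines primary patency as a time. SAP 2.19 does not say whether it is tabulated at the interim as lost yes/no or as a mean or median time.

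**Final**
- SAP 2.10 plans counts and percentages for the CEA primary endpoint.
- For the non-CEA primary endpoint, SAP 2.11 says "A Kaplan-Meier (KM) survival curve for primary patency will be estimated". SAP 2.12 to 2.16 and 2.18 plan curves for most secondary endpoints.
- Neither document mentions a confidence interval or standard error for any rate or curve, or a censoring rule.

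**The concern.** A percentage such as 0 of 40 reads very differently if most patients are four months past surgery than if many left hospital last week. The planned interim table mixes the two. The final analysis splits adverse events at 30 days (SAP 2.17), but 2.19 drops timing splits at the interim, where follow-up is most uneven. The result is meant to inform enrollment and possible changes to the study, so its reader needs to know what period each rate covers and how many patients were observed through it.

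The second issue runs through the whole study. It has a single arm, no hypothesis and, by SAP 2.20, a sample size without a formal statistical basis. An interval is then the natural statement of what the data can exclude, and none is planned, even for the primary endpoints.

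**Working it through.** **The plan's own figure.** The documents give no interim n, accrual pattern, event rate or precision target. The one sample-size figure, about 166 consented, reproduces as 100 / (0.67 × 0.90) = 165.8, but says nothing about precision. Everything below rests on assumptions beyond the 0-to-5-month range.

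**1. Crude percentage against 6-month risk R.** Expected crude proportion = ∫ F(t) g(t) dt over 0 to 5 months. F is cumulative risk and g the density of follow-up: uniform 1/5, back-loaded (recent operations dominate) 2(5−t)/25, front-loaded 2t/25.

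Uniform accrual worked through:
- Constant hazard, R = 10%: h = −ln(0.90)/6 = 0.01756; crude = 1 − (1 − e^(−5h))/(5h) = 4.3%; ratio 0.43.
- Half of events evenly in month 1, the rest over months 1 to 6: (0.25 + 2 + 0.8)/5 = 0.61.
- All events in month 1: (0.5 + 4)/5 = 0.90.

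| Crude ÷ 6-month risk | Uniform | Back-loaded | Front-loaded |
|---|---|---|---|
| Constant hazard, R = 5 to 30% | 0.42–0.45 | 0.28–0.31 | 0.56–0.59 |
| Half in month 1 | 0.61 | 0.49 | 0.73 |
| All in month 1 | 0.90 | 0.81 | 0.99 |

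Against day-77 risk (the early edge of the 3-month visit window), the crude figure lies between 0.65 and 1.30 times the true value. Even the direction depends on the time point a reader has in mind.

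**2. Patients with no post-discharge visit yet** (visit at 1 month): 1/5 = 20% uniform, 1 − (4/5)² = 36% back-loaded, (1/5)² = 4% front-loaded.

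**3. Patients a fixed-time estimate would rest on**, before removing events. Followed to the data cut, the 1-month shares are 0.80, 1 − 0.36 = 0.64 and 1 − 0.04 = 0.96 (day 30 is practically the same). The 3-month shares are 2/5 = 0.40, (2/5)² = 0.16 and 1 − (3/5)² = 0.64. The last-visit rows come from simulation, with visits uniform within ±14 days.

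| Share at risk | Uniform | Back-loaded | Front-loaded |
|---|---|---|---|
| Day 30, to data cut | 0.80 | 0.64 | 0.96 |
| Day 30, to last visit | 0.58 | 0.37 | 0.79 |
| 3 months, to data cut | 0.40 | 0.16 | 0.64 |
| Day 90, to last visit | 0.20 | 0.07 | 0.32 |

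With an assumed 40 interim patients and uniform accrual, that is about 32 or 23 at day 30 and 16 or 8 at 3 months. Day 30 is workable; 3 months may not be.

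**4. Censoring rule.** Serious and vascular events reach the sponsor within 24 hours of becoming known (Protocol 4.3), while event-free status is confirmed at visits. If events count to the data cut but event-free patients are censored at last contact, simulated Kaplan-Meier risk at day 77 is 1.07 to 1.86 times the truth (6-month risk 10%, three accrual patterns, three hazard shapes). Cutting events and censoring at the same point gives 0.99 to 1.01.

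**5. Exact 95% limits.** For no events, the upper limit is 1 − 0.025^(1/n).
- Interim, assumed n: 0/20, 0–16.8%; 0/40, 0–8.8%; 0/60, 0–6.0%; 2/40, 0.6–16.9%.
- Final: 0/50 CEA patients (assumed n), 0–7.1%; 5/100, 1.6–11.3%.

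**The case against.** - *Reading the crude figures as wrong.* A reader might infer this. The documents do not support it: 2.19 does not claim to estimate 6-month risk, the Protocol is open about the follow-up range, and events to date is a legitimate summary. The 6-month comparison shows only how far the figure could mislead if read that way.
- *Saying nobody could tell low risk from short follow-up.* That goes too far. With SAP 1.1 extending the document to the interim, by-visit statistics, the disposition table (2.3) and the listings show roughly who has reached which visit. A number at risk and a fixed-time risk remain absent.
- *The remedy can be worse than the problem.* This stands for a mixed censoring rule, whose upward lean can exceed the error of the crude figure as a guide to the same time point. It does not apply when events and censoring share a cut-off.
- *Intervals can be computed from the counts.* True for percentages, but not for Kaplan-Meier estimates. The sponsor's report should not leave the primary endpoint's precision to its readers.
- *Patency is already a yes/no item on the Follow-Up form.* So the gap in 2.19 is small, and one sentence closes it.
- *Little hangs on the interim.* Correct: no threshold or test is attached, and expedited event reporting continues regardless. This limits the weight of the point without removing it.

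**Conclusion.** The point holds in two parts. First, the interim percentages pool follow-up of unequal length and refer to no common window, and the other planned outputs only partly make up for it. The size cannot be fixed from the documents. Under the assumed accrual and hazard shapes, the crude figure is 0.28 to 0.99 of 6-month risk, so the gap is large if hazard is constant and recent operations dominate, and negligible if events are almost all perioperative and most patients were treated early. Second, no interval is planned for any rate or curve at either analysis; this follows directly from the text. The documents do not support a claim that the interim is invalid or would force a wrong decision. This is an inexpensive improvement of minor to moderate weight.

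**What to change.** 1. **SAP 2.19.** Beside each crude percentage, give the follow-up distribution and a Kaplan-Meier estimate with 95% interval and number at risk at day 30, the study's own early/late cut. Add 3 months only if enough patients remain at risk, with the minimum stated beforehand.
2. **One cut-off for events and censoring.** Use either the last completed visit for both or, if reporting between visits is taken as complete, the data cut for both; run the other as a check. Do not count events to the data cut while censoring event-free patients at last contact. Under the visit rule, a patient who dies before a visit needs the date that visit was due; otherwise the death falls after the cut and is lost.
3. **Patency at the interim.** State that it is summarised as lost yes/no plus Kaplan-Meier, not as a mean or median time.
4. **Both analyses.** Add exact 95% intervals to the endpoint percentages, including the CEA endpoint in 2.10, and 95% intervals to the Kaplan-Meier estimates in 2.11 to 2.18.

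The cost is SAP wording and a little code. The case report forms already hold the dates of surgery, visits, patency loss, adverse events, explant and discontinuation. Restenosis has no onset date on the Follow-Up form, so the SAP should name the imaging or visit date. The visible downsides are wide intervals and few patients at risk at 3 months. Both describe the data accurately.
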